#### 14.2.3.2.9 Sensitivity analyses

This section outlines the possible event and censoring dates for progression, as well as addresses the issues of missing tumor assessments during the study. For instance, if one or more assessment visits are missed prior to the progression event, to what date should the progression event be assigned? And should progression event be ignored if it occurred after a long period of a subject being lost to follow-up? It is important that the protocol and RAP specify the primary analysis in detail with respect to the definition of event and censoring dates and also include a description of one or more sensitivity analyses to be performed.

Based on definitions outlined in Section 14.2.3.2.7, and using the draft FDA guideline on endpoints (Clinical Trial Endpoints for the Approval of Cancer Drugs and Biologics, April 2005) as a reference, the following analyses can be considered:

**Table 14-9 Options for event dates used in PFS, TTP, duration of response**

Situation		Options for end-date (progression or censoring)  (1) = default unless specified differently in the protocol or RAP	Outcome
A	No baseline assessment	(1) Date of randomization/start of treatment 	Censored
B	Progression at or before next scheduled assessment	(1) Date of progression (2) Date of next scheduled assessment 	Progressed Progressed
C1	Progression or death after exactly one missing assessment	(1) Date of progression (or death) (2) Date of next scheduled assessment 	Progressed Progressed
C2	Progression or death after two or more missing assessments	(1) Date of last adequate assessment  (2) Date of next scheduled assessment  (3) Date of progression (or death)	Censored Progressed Progressed
D	No progression	(1) Date of last adequate assessment	Censored

Situation		Options for end-date (progression or censoring)  (1) = default unless specified differently in the protocol or RAP	Outcome
E	Treatment discontinuation due to 'Disease progression' without documented progression, i.e. clinical progression based on investigator claim	(1) Ignore clinical progression and follow situations above (2) Date of discontinuation (visit date at which clinical progression was determined)	As per above situations  Progressed
F	New anticancer therapy given	(1) Ignore the new anticancer therapy and follow situations above (ITT approach) (2) Date of last adequate assessment prior to new anticancer therapy (3) Date of secondary anti-cancer therapy (4) Date of secondary anti-cancer therapy	As per above situations Censored  Censored Event
G	Deaths due to reason other than deterioration of 'Study indication'	(1) Date of last adequate assessment	Censored (only TTP and duration of response)

1. =Definitions can be found in [Section 14.2.3.2.7](#)
2. =After the last adequate tumor assessment. "Date of next scheduled assessment" is defined in [Section 14.2.3.2.7](#).
3. =The rare exception to this is if the subject dies no later than the time of the second scheduled assessment as defined in the protocol in which case this is a PFS event at the date of death.

The primary analysis and the sensitivity analyses must be specified in the protocol. Clearly define if and why options (1) are not used for situations C, E and (if applicable) F.

[figure not shown]
Situations C (C1 and C2): Progression or death after one or more missing assessments: The primary analysis is usually using options (1) for situations C1 and C2, i.e.

- (C1) taking the actual progression or death date, in the case of only one missing assessment.
- (C2) censoring at the date of the last adequate assessment, in the case of two or more consecutive missing assessments.

In the case of two or missing assessments (situation C2), option (3) may be considered jointly with option (1) in situation C1 as sensitivity analysis. A variant of this sensitivity analysis consists of backdating the date of event to the next scheduled assessment as proposed with option (2) in situations C1 and C2.

**Situation E: Treatment discontinuation due to 'Disease progression' without documented progression:** By default, option (1) is used for situation E as subjects without documented PD should be followed for progression after discontinuation of treatment. However, option (2) may be used as sensitivity analysis. If progression is claimed based on clinical deterioration instead of tumor assessment by e.g. CT-scan, option (2) may be used for indications with high early progression rate or difficulties to assess the tumor due to clinical deterioration.

**Situation F: New cancer therapy given:** the handling of this situation must be specified in detail in the protocol. However, option (1) (ITT) is the recommended approach; events documented after the initiation of new cancer therapy will be considered for the primary analysis i.e. progressions and deaths documented after the initiation of new cancer therapy

would be included as events. This will require continued follow-up for progression after the start of the new cancer therapy. In such cases, it is recommended that an additional sensitivity analysis be performed by censoring at last adequate assessment prior to initiation of new cancer therapy.

Option (2), i.e. censoring at last adequate assessment may be used as a sensitivity analysis. If a high censoring rate due to start of new cancer therapy is expected, a window of approximately 8 weeks performed after the start of new cancer therapy can be used to calculate the date of the event or censoring. This should be clearly specified in the analysis plan.

In some specific settings, local treatments (e.g. radiation/surgery) may not be considered as cancer therapies for assessment of event/censoring in PFS/TTP/DoR analysis. For example, palliative radiotherapy given in the trial for analgesic purposes or for lytic lesions at risk of fracture will not be considered as cancer therapy for the assessment of BOR and PFS analyses. The protocol should clearly state the local treatments which are not considered as anti-cancer therapies in the PFS/TTP/DoR analysis.

The protocol should state that tumor assessments will be performed every x weeks until radiological progression irrespective of initiation of new anti-cancer therapy. It is strongly recommended that a tumor assessment is performed before the subject is switched to a new cancer therapy.

### **Additional suggestions for sensitivity analyses**

Other suggestions for additional sensitivity analyses may include analyses to check for potential bias in follow-up schedules for tumor assessments, e.g. by assigning the dates for censoring and events only at scheduled visit dates. The latter could be handled by replacing in Table 14-8 the “Date of last adequate assessment” by the “Date of previous scheduled assessment (from baseline)”, with the following definition:

- **Date of previous scheduled assessment (from baseline)** is the date when a tumor assessment would have taken place, if the protocol assessment scheme was strictly followed from baseline, immediately before or on the date of the last adequate tumor assessment.

In addition, analyses could be repeated using the Investigators’ assessments of response rather than the calculated response. The need for these types of sensitivity analyses will depend on the individual requirements for the specific study and disease area and have to be specified in the protocol or RAP documentation.

[figure not shown]
#### **14.2.4 Data handling and programming rules**

The following section should be used as guidance for development of the protocol, data handling procedures or programming requirements (e.g. on incomplete dates).

##### **14.2.4.1 Study/project specific decisions**

For each study (or project) various issues need to be addressed and specified in the protocol or RAP documentation. Any deviations from protocol must be discussed and defined at the latest in the RAP documentation.

The proposed primary analysis and potential sensitivity analyses should be discussed and agreed with the health authorities and documented in the protocol (or at the latest in the RAP documentation before database lock).

#### **14.2.4.2 End of treatment phase completion**

Subjects **may** voluntarily withdraw from the study treatment or may be taken off the study treatment at the discretion of the investigator at any time. For subjects who are lost to follow-up, the investigator or designee should show "due diligence" by documenting in the source documents steps taken to contact the subject, e.g., dates of telephone calls, registered letters, etc.

The end of treatment visit and its associated assessments should occur within 7 days of the last study treatment.

Subjects may discontinue study treatment for any of the following reasons:

- Adverse event(s)
- Lost to follow-up
- Physician decision
- Pregnancy
- Protocol deviation
- Technical problems
- Subject/guardian decision
- Progressive disease
- Study terminated by the sponsor
- Non-compliant with study treatment
- No longer requires treatment
- Treatment duration completed as per protocol (optional, to be used if only a fixed number of cycles is given)

Death is a reason which "*must*" lead to discontinuation of subject from trial.

#### **14.2.4.3 End of post-treatment follow-up (study phase completion)**

End of post-treatment follow-up visit will be completed after discontinuation of study treatment and post-treatment evaluations but prior to collecting survival follow-up.

Subjects may provide study phase completion information for one of the following reasons:

- Adverse event
- Lost to follow-up
- Physician decision
- Pregnancy
- Protocol deviation
- Technical problems
- Subject/guardian decision
- Death
- Progressive disease
- Study terminated by the sponsor

#### **14.2.4.4 Medical validation of programmed overall lesion response**

In order to be as objective as possible the RECIST programmed calculated response assessment is very strict regarding measurement methods (i.e. any assessment with more or

less sensitive method than the one used to assess the lesion at baseline is considered UNK) and not available evaluations (i.e. if any target or non-target lesion was not evaluated the whole overall lesion response is UNK unless remaining lesions qualified for PD). This contrasts with the slightly more flexible guidance given to local investigators (and to the central reviewers) to use expert judgment in determining response in these type of situations, and therefore as a consequence discrepancies between the different sources of response assessment often arise. To ensure the quality of response assessments from the local site and/or the central reviewer, the responses may be re-evaluated by clinicians (based on local investigator data recorded in eCRF or based on central reviewer data entered in the database) at Novartis or external experts. In addition, data review reports will be available to identify assessments for which the investigators' or central reader's opinion does not match the programmed calculated response based on RECIST criteria. This may be queried for clarification. However, the investigator or central reader's response assessment will never be overruled.

If Novartis elect to invalidate an overall lesion response as evaluated by the investigator or central reader upon internal or external review of the data, the calculated overall lesion response at that specific assessment is to be kept in a dataset. This must be clearly documented in the RAP documentation and agreed before database lock. This dataset should be created and stored as part of the 'raw' data.

Any discontinuation due to 'Disease progression' without documentation of progression by RECIST criteria should be carefully reviewed. Only subjects with documented deterioration of symptoms indicative of progression of disease should have this reason for discontinuation of treatment or study evaluation.

#### **14.2.4.5 Programming rules**

The following should be used for programming of efficacy results:

##### **14.2.4.5.1 Calculation of 'time to event' variables**

Time to event = end date - start date + 1 (in days)

[figure not shown]
When no post-baseline tumor assessments are available, the date of randomization/start of treatment will be used as end date (duration = 1 day) when time is to be censored at last tumor assessment, i.e. time to event variables can never be negative.

##### **14.2.4.5.2 Incomplete assessment dates**

All investigation dates (e.g. X-ray, CT scan) must be completed with day, month and year.

If one or more investigation dates are incomplete but other investigation dates are available, this/these incomplete date(s) are not considered for calculation of the assessment date (and assessment date is calculated as outlined in [Section 14.2.3.2.7](#)). If all measurement dates have no day recorded, the 1st of the month is used.

If the month is not completed, for any of the investigations, the respective assessment will be considered to be at the date which is exactly between previous and following assessment. If a previous and following assessment is not available, this assessment will not be used for any calculation.

#### 14.2.4.5.3 Incomplete dates for last known date subject alive or death

All dates must be completed with day, month and year. If the day is missing, the 15th of the month will be used for incomplete death dates or dates of last contact.

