## **Overall Survival**

Overall survival (OS) is defined as the time from date of randomization to date of death due to any cause. If a subject is not known to have died, then OS will be censored at the latest date the subject was known to be alive (on or before the cut-off date).

OS will be analyzed in the FAS population. The OS distribution will be estimated using the Kaplan-Meier method, and the Kaplan-Meier curves, medians and 95% confidence intervals of the medians will be presented for each treatment group.

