##### **End dates**

The end dates which are used to calculate ‘time to event’ variables are defined as follows:

- Date of death (during treatment as recorded on the treatment completion page or during follow-up as recorded on the study evaluation completion page or the survival follow-up page).
- Date of progression is the first assessment date at which the overall lesion response was recorded as progressive disease.
- Date of last adequate tumor assessment is the date the last tumor assessment with overall lesion response of CR, PR or SD which was made before an event or a censoring reason occurred. In this case the last tumor evaluation date at that assessment is used. If no post-baseline assessments are available (before an event or a censoring reason occurred) the date of randomization/start of treatment is used.
- Date of next scheduled assessment is the date of the last adequate tumor assessment plus the protocol specified time interval for assessments. This date may be used if back-dating is considered when the event occurred beyond the acceptable time window for the next tumor assessment as per protocol.

**Example** (if protocol defined schedule of assessments is 3 months): tumor assessments at baseline - 3 months - 6 months - missing - missing - PD. Date of next scheduled assessment would then correspond to 9 months.

- Date of discontinuation is the date of the end of treatment visit.
- Date of last contact is defined as the last date the subject was known to be alive. This corresponds to the latest date for either the visit date, lab sample date or tumor assessment date. If available, the last known date subject alive from the survival follow-up page is used. If no survival follow-up is available, the date of discontinuation is used as last contact date.
- Date of secondary anti-cancer therapy is defined as the start date of any additional (secondary) anti-cancer therapy or surgery.

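### Appendix 2 sets a death date with a missing day to the 15th of the month without any ordering bound, so the imputed death can precede a known-alive or start date, or fall after the cut-off

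*Protocol*

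**What the plan says.** Section 14.2.4.5.3 first asks for complete dates. It then provides that, if the day is missing, the 15th "of the month will be used for incomplete death dates or dates of last contact". No condition follows.

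The sections that use such a date are these:

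- Section 14.2.4.5.1 gives the formula: "Time to event = end date - start date + 1 (in days", closing bracket omitted here. It also says that the start date serves as end date when there is no post-baseline scan, "when time is to be censored at last tumor assessment, i.e. time to event variables can never be negative".
- Section 10.5.2 defines OS: "Overall survival (OS) is defined as the time from date of randomization to date of death due to any cause". In the non-randomized section of the study, Section 10 replaces randomization by the first dose. For a subject not known to have died, "OS will be censored at the latest date the subject was known to be alive (on or before the cut-off date", closing bracket again omitted.
- Section 10.5.2 also counts death from any cause as a PFS event, so the same imputed date can enter PFS.
- Section 14.2.3.2.7 (End dates) says "Date of last contact is defined as the last date the subject was known to be alive", and then prefers the date on the survival follow-up page where there is one.

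Section 14.2.4.5 says its rules should be used when efficacy results are programmed. Section 14.2.4 calls the material guidance, and Section 14.2.4.5.5 asks that standard programs be adapted to each study.

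**The concern.** A mid-month default is ordinary practice, but it normally carries an ordering check, because the month of death often holds other complete dates such as a visit, a laboratory sample, a scan or the start of treatment. Without the check, a program that follows the text can date a death before the subject was last seen alive, or before the survival clock started. If the cut-off falls early in the month, a death known to have occurred by then can be dated after it.

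Survival status is collected by telephone every 12 weeks after safety and efficacy follow-up (Section 7.1.9), so deaths reported by month only are foreseeable. At stake are individual OS times and those PFS times that end in death. Some would be impossible values, and others would contradict dates already in the database.

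**Working it through.** The protocol states no figure on this point, so there is none to reproduce. The check applies its own two rules, day = 15 (Section 14.2.4.5.3) and time = end - start + 1 (Section 14.2.4.5.1), to example dates. The calendar dates are assumptions.

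**1. Death before the start date.** Start on day d, death in the same month, day missing:

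OS = 15 - d + 1 = 16 - d

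| Start day d | OS (days) |
|---|---|
| 15 | 1 |
| 16 | 0 |
| 17 | -1 |
| 20 | -4 |
| 31 | -15 |

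For a start on 20 March, the true value must lie between 1 and 12 days. Given a same-month death with the day missing, the start days that give OS of zero or less number 13 of 28 (46%), 15 of 30 (50%) or 16 of 31 (52%), depending on month length.

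**2. Death before a documented known-alive date.** Start 1 September 2020, visit on 25 March 2021, death recorded as March 2021. There are 181 days from 1 September to 1 March.

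- Imputed death on 15 March: 181 + 14 + 1 = 196 days.
- Known alive on 25 March: 181 + 24 + 1 = 206 days.

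The recorded survival is 10 days shorter than survival already documented.

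**3. Death after the cut-off.** Same start, cut-off 10 March 2021, death known to have occurred in March by the cut-off.

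- Imputed death: 196 days.
- Largest possible value at the cut-off: 181 + 9 + 1 = 191 days.

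This can arise for any cut-off on days 1 to 14.

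**4. Largest error.** A true death on day 1 is dated 14 days late. A true death on day 31 is dated 16 days early.

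**5. How often case 2 arises, given a missing day.** Assume a 30-day month, a death day uniform on 1 to 30, and a gap from last contact to death uniform on 0 to G days. Last contact falls after the 15th when death day minus gap is at least 16. For death days 16 to 30 the qualifying gaps number 1, 2, ..., 15, so there are 120 pairs in all.

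| G (days) | Pairs | Share |
|---|---|---|
| 14 | 30 × 15 = 450 | 120/450 = 26.7% |
| 28 | 30 × 29 = 870 | 120/870 = 13.8% |
| 84 | 30 × 85 = 2550 | 120/2550 = 4.7% |

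Among the affected records the imputed death precedes last contact by 1 to 15 days, with a mean of 680/120 = 5.7 days. G = 28 corresponds to the 28-day treatment cycle and G = 84 to the 12-weekly survival calls. All three shares are conditional on the day being missing, and the protocol gives no rate for that.

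**The case against.** The strongest reply is that ordering checks on partial dates belong in the statistical analysis plan (SAP). Section 14.2.1 says the data-handling section is to be referred to in the SAP, Section 14.2.4 describes it as guidance, Section 14.2.4.1 lets study-specific issues be settled in the analysis-plan documentation, and Section 14.2.4.5.5 requires adaptation. The SAP is not shown and may contain the bound. It is also fair that complete dates are required in the first place and that Section 9.4 provides queries for missing values.

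This limits the weight of the point but does not remove it. The protocol does not leave the matter open. It fixes the 15th, and Section 14.2.4.5 directs that the rule be used in programming efficacy results. None of the sections cited supplies a bound. The neighbouring Section 14.2.4.5.2 keeps date order when the month of a scan is missing, by placing the scan between the assessments on either side.

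A reader might infer more than the protocol supports in four respects:

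- **That last-contact dates are equally unbounded.** Section 10.5.2 censors OS at the latest known-alive date on or before the cut-off, so a later complete contact should prevail. What remains is a tension with Section 14.2.3.2.7, where a survival-page date, possibly imputed, is preferred when available.
- **That Section 14.2.4.5.1 is contradicted outright.** The words "time to event variables can never be negative" explain the 1-day convention for censoring when there is no post-baseline scan. They are not a rule about imputed deaths, although a survival time of zero or less plainly goes against their sense.
- **That deaths would be misplaced between on-treatment and post-treatment periods.** Section 10.5.3.1 has its own default, assigning data with unclear dates to the on-treatment period, and the Appendix 2 rule is for efficacy programming.
- **That the situation is common in this population.** No figure in the protocol supports that.

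**Conclusion.** The point holds for death dates, as a minor one. The rule as written can produce an OS of zero or less, a death before a documented known-alive date, or a death after an early-month cut-off. These follow directly from the two stated rules and need no distributional assumption.

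The size is limited. The imputed date is off by at most about two weeks, only death records with a missing day are affected, and OS and PFS are summarized descriptively by Kaplan-Meier. The effect on median OS should be small unless many days are missing. Death in the month of start with an unknown day should be rare. Confirmed ORR, the only endpoint formally tested, does not depend on these dates. The shares of 27%, 14% and 5% rest on the uniform assumptions above. After treatment, with 12-weekly calls, the lowest is the most relevant.

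**What to change.** Replace the sentence in Section 14.2.4.5.3 by wording such as:

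> If the day of death is missing, use the 15th of the recorded month or, if later, the last complete date on which the subject was known alive or the randomization/first-dose date, staying within the recorded month. For a death known to have occurred on or before the cut-off, the imputed date is not later than the cut-off. A partial last-contact date never replaces a later complete date on which the subject was known alive (consistent with Section 10.5.2).

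Three details matter. The floor is the last known-alive date itself, because the day after it could leave the recorded month: a subject seen on 31 March who died in March would be dated 1 April. The start date is named as a floor, so that OS is at least 1 day. The cap applies only to deaths known to have occurred by the cut-off, because a blanket cap could turn a later death into an event at the cut-off.

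Under this wording the three examples give 1 day instead of -4, 206 instead of 196, and 191 instead of 196.

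The cost is a few lines of text in Appendix 2 and a line or two of program code. No data collection, sample size or primary analysis changes. If the SAP already contains such a bound, a cross-reference to it is enough.
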